10. APPENDICES

10.1. Derivation for Endpoints

10.1.1. Cumulative IV Opioid Consumption

The cumulative amount of IV opioid use will be standardized using morphine equivalent units (MEU). The conversion to MEU will be performed using the formula below:

$$\text{Cumulative MEU} = \sum_{i=1}^n \frac{(\text{Total dose of the } i^{\text{th}} \text{ IV medication in mg})}{(E_i)} \times 10 \quad (1)$$

where E_i is the equianalgesic dose for the i^{th} IV medication.

Alternatively the cumulative MEU could be calculated using the following formula:

$$\text{Cumulative MEU} = \sum_{i=1}^n (\text{Total dose of the } i^{\text{th}} \text{ IV medication in mg}) \times CF_i \quad (2)$$

where CF_i is the conversion factor for the i^{th} IV medication.

Equianalgesic doses for opioids, shown in below table, were obtained from the VHA/DoD Guideline for the Management of Postoperative Pain
(https://www.healthquality.va.gov/guidelines/Pain/pop/pop_fulltext.pdf).

Equianalgesic Doses for IV Opioids

Medication	Route	Equianalgesic Dose (mg)	Conversion Factor (CF) to Give Morphine Equivalent*
Buprenorphine	IV	0.3	33.33
Butorphanol	IV	2	5
Codeine	IV	120	0.083
Desocine	IV	10	1
Fentanyl	IV	0.1**	100
Hydromorphone	IV	1.4	7.14
Levorphanol	IV	2	5
Meperidine	IV	87.5**	0.114
Methadone	IV	10	1
Morphine	IV	10	1
Nalbuphine	IV	10	1
Oxymorphone	IV	1	10
Pentazocine	IV	30	0.333

*Conversion Factor = 10 / (Equianalgesic Dose) which is based on 10mg morphine.

** The morphine conversions for doses administered via IM or IV are equivalent. Reference:

<https://cha.com/wp-content/uploads/2018/04/Colorado-Opioid-Safety-Pilot-Conversion-Table-1.pdf>.

Once the cumulative opioid usage is expressed in MEU, this dosage will be normalized by dividing by the subject's body weight (ie, MEU/kg).

- For cumulative IV opioid consumption for the treated VOC all administered IV opioid doses after the start of the first infusion (loading dose) of study drug while the subject is hospitalized, will be counted using formula (1).
- For cumulative IV opioid consumption within the first 24 hours post-loading dose of study drug, the total computed in formula (1) will be from the start of the first infusion (loading dose) of study drug to 24 hours after the start of the first infusion (loading dose) of study drug.

10.1.2. Hourly IV Opioid Use in MEU/kg/hour (every 4 hours, for the first 48 hours post-loading dose of study drug)

[figure not shown]
[figure not shown]
[figure not shown]
[figure not shown]
Hourly IV opioid use (based on data collected every 4 hours) will be calculated by first totaling the amount of IV opioids administered in increments of 4 hours for the first 48 hours after the start of the first infusion (loading dose) of study drug. The amount of IV opioid use will be standardized using morphine equivalent units (MEU) (see [Section 10.1.1](#)). Hourly IV opioid use will then be calculated by dividing the total amount of opioids used within each 4-hour period by 4. This quantity will then be normalized by dividing by the subject's body weight. Consequently, hourly IV opioid use will be expressed in units of MEU /kg/hour. A subject will be assigned an IV opioid use of 0 for any 4-hour period in which the subject did not receive any IV opioids. For subjects who are discharged less than 48 hours after the first infusion (loading dose) of study drug, the subject's hourly IV opioid use will be assigned a value of 0 for any 4-hour interval within the 48-hour period that occurs after the subject has been discharged from hospital.

10.1.3. Daily IV Opioid Use

In this study, subjects may receive study drug for up to 8 days (up to 15 doses of study drug: 1 loading dose and a maximum of 14 maintenance doses). In the Phase 2 study, 79% of subjects were discharged from hospital within 8 days. Therefore, daily IV opioid use will be analyzed from Day 1 through Day 8. The subject's daily opioid use will be the total amount of opioid used in increments of 24 hours starting at the start of the first infusion (loading dose) of study drug and continuing for the entire duration of the subject's hospitalization or through the Day 8 / Hour 24 time point. The amount of IV opioid received will be standardized using morphine equivalent units (MEU) and normalized by the subject's body weight (see [Section 10.1.1](#)). A subject will be assigned an IV opioid use of 0 for any day in which the subject did not receive any IV opioids. For subjects who are discharged before Day 8, the subject's daily IV opioid use will be assigned a value of 0 for any 24-hour interval within the 8-day period that occurs after the subject has been discharged from hospital.

10.2. Definition and Use of Visit Windows in Reporting

Statistical Analysis Plan B5201002 v5

Page 48 of 56

090177e19152273c\Approved\Approved On: 12-Jul-2019 12:42 (GMT)

Other Endpoints:

For other endpoints, such as physical examination and vital signs, the data will be analyzed and presented based on the CRF recorded study visit time point. If there is more than one record for the same subject at the same time point, the most clinically extreme value will be

used as the observation for that time point. All observations will, however, be included in the listings.

10.3. Shift Tables for Reporting of Laboratory Test Results

For the lab variables included in the table below, shift tables will be generated showing the shift at End of treatment and at the Day 35 post-discharge follow-up visit, from the grade category at Baseline.

Lab parameters	Grade				
	0	1	2	3	4
Hemoglobin	>11g/dl	>9 to 11 g/dl	>7 to 9 g/dl	5 to 7 g/dl	<5g/dl
Reticulocyte Count	<1%	1 to 5%	>5 to 10%	>10 to 20%	>20%
Leukocyte (WBC)	≤ ULN	>ULN to 15,000/mm ³	>15,000 to 20,000/mm ³	>20,000 to 50,000/mm ³	>50,000/mm ³
Absolute Neutrophil Count (ANC)	≥ LLN	<LLN to 1,500/mm ³	<1,500 to 1,000 /mm ³	<1,000 to 500/mm ³	<500/mm ³
Blood urea nitrogen (BUN)	≤ ULN	>ULN to 1.5 x ULN	>1.5 to 3.0 x ULN	>3.0 x ULN	>6.0 x ULN
Creatinine	≤ ULN	>ULN to 1.5 x ULN	>1.5 to 3.0 x ULN	>3.0 x ULN	>6.0 x ULN
Lactate dehydrogenase (LDH)	≤ ULN	>ULN to 3.0 x ULN	>3.0 to 5.0 x ULN	>5.0 to 20.0 x ULN	>20.0 x ULN
Alanine transaminase (ALT/SGPT)	≤ ULN	>ULN to 3.0 x ULN	>3.0 to 5.0 x ULN	>5.0 to 20.0 x ULN	>20.0 x ULN
Aspartate aminotransferase (AST/SGOT)	≤ ULN	>ULN to 3.0 x ULN	>3.0 to 5.0 x ULN	>5.0 to 20.0 x ULN	>20.0 x ULN
Fractionated bilirubin	≤ ULN	>ULN to 1.5 x ULN	>1.5 to 3.0 x ULN	>3.0 to 10.0 x ULN	>10.0 x ULN
Urine Protein	Negative (0-15 mg/dL)	Trace (>15-30 mg/dL)	1+ (>30-100 mg/dL)	2+ (>100-300 mg/dL)	3+ or 4+ (>300 mg/dL)
Platelet	≥ 150K	≥ 100K to <150K	≥ 50K to <100K	<50K	
eGFR	≥ 90 mL/min/1.73 m ²	≥ 60 to < 90 mL/min/1.73 m ²	≥ 30 to < 60 mL/min/1.73 m ²	≥ 15 to < 30 mL/min/1.73 m ²	<15 mL/min/1.73 m ²

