In these three Phase 1 studies there were no clinically significant electrocardiogram (ECG) or physical examination findings. With one exception, all adverse events in subjects receiving rivilansel were Grades 1 or 2. Severe symptomatic anemia (Grade 4) that occurred in 1 subject with stable SCD was considered to be remotely related to the study medication, and resolved with therapy. No serious adverse events were reported in these studies.

A randomized, placebo-controlled Phase 2 trial (GMI-1070-201), evaluating the efficacy, safety, and pharmacokinetics of multiple IV doses of rivilansel in 76 subjects 12 to 60 years of age who were hospitalized for sickle cell VOC is now complete. This study included two dosing schedules; the first cohort received 20 mg/kg loading dose, then 10 mg/kg every 12 hours for up to 7 days, (maximum 15 doses) and the second cohort received 40 mg/kg loading dose, then 20 mg/kg every 12 hours for up to 7 days, (maximum 15 doses).

In the phase 2 study, the primary endpoint, time to resolution of VOC, was shorter for the rivilansel treated group versus the placebo group. The mean time to VOC resolution was 110 hours and 148 hours for the rivilansel treated group and the placebo group, respectively. Treatment with rivilansel was also associated with improvement in clinical measures of VOC. The rivilansel treatment group had a shorter median time to transition from parenteral to oral pain medications, time to discharge from the hospital, and time to first sustained reduction in VAS pain score. Mean use of opioid analgesics during hospitalization was also lower in the rivilansel treated group.

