4.2. Exclusion Criteria

Subjects presenting with any of the following, from the time of VOC/Treatment-Ready Screening up to the time of randomization unless otherwise stated, will not be included in the study:

1. Serious systemic infection, evidenced by clinical signs and symptoms, and/or microbiological investigations, consistent with this diagnosis. Subjects with fever $< 39^{\circ}\text{C}$ (102.2°F) may be considered for enrollment if in the opinion of the investigator there is no evidence of any serious systemic infection. Subjects with fever $\geq 39^{\circ}\text{C}$ (102.2°F) are excluded.
2. Subjects presenting with the following clinical risk factors of acute chest syndrome:
 - Hypoxia – defined as O₂ saturation of $<90\%$ (by pulse oximetry) on room air on 2 separate readings 15 minutes apart, or single value of PaO₂ <60 mmHg on arterial blood gas,
and/or
 - Hemoglobin <5 gm/dL.

3. Acute chest syndrome, at the time of presentation, as defined by the National Institutes of Health (NIH) treatment guidelines:^{24,25}

New pulmonary infiltrate involving at least one complete lung segment consistent with the presence of alveolar consolidation, (excluding atelectasis) AND one or more of the following:

- Chest pain;
- Temperature $>38.5^{\circ}$ C;
- Tachypnea;
- Wheezing or rales;
- Cough.

4. SCD pain atypical of VOC, including hepatic or splenic sequestration, cholecystitis, or pneumonia.

5. At the time of presentation:

- acute stroke, or
- severe avascular necrosis of the hip/shoulder when the presenting pain is only in the affected hip/shoulder.

6. Estimated glomerular filtration rate (eGFR) ≤ 60 mL/min/1.73 m² (refer to [Appendix 1](#) for calculation).

7. History consistent with rapidly progressive decrease or decrement in renal function, in the opinion of the investigator.

8. Alanine aminotransferase (ALT/SGPT) >3 times the upper limit of normal (X ULN) (based on clinic laboratory normal range).

9. Platelets $<50,000/\text{mm}^3$.

10. Subjects currently receiving transdermal analgesics and/or the expectation that transdermal analgesics may be used during the study for treatment of this episode of VOC (see Section 5.8.2).

11. Recent (within the past 30 days) major surgery (see definition in [Section 4.3.2](#)), hospitalization for reasons other than VOC, documented serious infection requiring IV antibiotic treatment, or significant bleeding.

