5.8.5. Transfusion

In all cases, the medical judgment of the responsible physician will determine the course of treatment. The following suggestions are made for standardized management of transfusions in study subjects:

- Uncomplicated pain episodes generally do not require transfusion for treatment.
- Conditions that may develop during the course of the hospitalization which may require transfusion as determined by the physician might include, but are not limited to the following: acute neurologic event, severe ACS with significant oxygen requirement, unrelenting cases of priapism, severe anemia with cardiac decompensation, and/or symptomatic anemia (such as subjective shortness of breath or postural dizziness), worsening of anemia with an inadequate reticulocyte response, or splenic or hepatic sequestration.

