6.2.3. Visit 1, Day 2 through Day 8 (or End of Treatment)

While the subject is hospitalized, the following activities are to be performed on a daily basis, unless otherwise noted, until End of Treatment:

1. Record adverse events.
2. Record concomitant medications, including parenteral opioid use. Record IV opioid use approximately every 4 hours for the first 48 hours from the start time of the study drug loading dose.
3. Record concomitant non-drug treatments/procedures.
4. Collect vital signs (temperature [$^{\circ}$ Celsius], respiratory rate, pulse, blood pressure, and pulse oximetry).

[REDACTED]

[REDACTED]

7. Conduct a targeted physical exam, daily through 24 hours after last dose (if not discharged first), assessing the following at a minimum: skin, chest, respiratory, cardiovascular, abdominal, and musculoskeletal systems. Particular attention will be directed at areas affected by pain. Additional body systems may be examined at the discretion of the investigator.
8. Evaluate readiness-for-discharge criteria using the eClinRO web-based data capture system every 4 (± 1) hours during “daytime hours” only (defined as 6:01am to 10:00pm). Evaluate and capture data relevant to readiness-for-discharge criteria data in the eCRF as per data capture requirements (see [Section 7.1.1](#)). Refer to [Section 7.1.1](#) for details on the exact timing of the readiness-for-discharge assessments.

[REDACTED]

9. Administer study drug infusion every 12 (± 2) hours until criterion 1 of the readiness-for-discharge criteria (see [Section 7.1.1](#)) has been met, or up to 15 doses of study drug, whichever comes first. Record the date and time (24-hour clock) of the beginning and the end of each infusion.

[REDACTED]

■ [REDACTED]

■ [REDACTED]

The following End of Treatment procedures are to be performed within 24 hours after the last dose of study drug. This will occur prior to discharge, either on Day 8 or earlier.

1. Conduct a targeted physical exam, assessing the following at a minimum: skin, chest, respiratory, cardiovascular, abdominal and musculoskeletal systems. Particular attention will be directed at areas affected by pain. Additional body systems may be examined at the discretion of the investigator.
2. Collect vital signs (temperature [$^{\circ}$ Celsius], respiratory rate, pulse, blood pressure, and pulse oximetry).
3. Collect blood samples for:
 - Hematology panel (see [Table 3](#)); local laboratory;

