7.2.3. Clinical Laboratory Evaluation

Blood and urine samples will be collected at each specified study visit (see [Table 1](#), Schedule of Activities). Unscheduled clinical labs may be obtained at any time during the study to assess any perceived safety concerns or in accordance with the guidelines for subject safety monitoring and discontinuation. Clinically significant abnormal findings should be recorded as AEs per [Section 8.5](#).

The following laboratory tests will be performed locally during the study at the VOC/Treatment-Ready Screening visit, End of Treatment, and the Day 35 Post-Discharge Follow-Up visit:

Table 3. Clinical Laboratory Evaluations – Local Laboratory	
Hematology	
Hemoglobin	Reticulocyte count
Hematocrit	Platelet count
Red blood cell (RBC) count	WBC count with differential
Serum Chemistry	
Blood urea nitrogen (BUN)	Alanine aminotransferase (ALT/SGPT)
Creatinine	Aspartate aminotransferase (AST/SGOT)
Electrolytes (Sodium, Potassium, Chloride and Bicarbonate) with glucose	Fractionated bilirubin
Lactate dehydrogenase (LDH)	
Urinalysis	
Protein	Blood
Glucose	Nitrite
Ketones	Leukocyte esterase
Estimated Glomerular Filtration Rate (eGFR) at VOC/Treatment-Ready Screening visit (calculated using age appropriate formula in Appendix 1)	

Note: A hemoglobin electrophoresis sample will be collected at the VOC/Treatment-Ready Screening visit and analyzed at the central laboratory only if the subject's diagnosis (ie, laboratory result by hemoglobin electrophoresis, HPLC, or genotype analysis) cannot be source documented.

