	C4	If a subject never received any IV hydration, then C4 is not applicable and will not be used in the TTRFD derivation; otherwise C4 is considered met at the latest stop date and time of IV hydration. For C4, if IV hydration use ended before the start of the first infusion (loading dose) of study drug, then C4 will be considered as having been met at the date and time of the start of first infusion (loading dose) of study drug.
	C5	If a subject never received any IV antibiotics, then C5 is not applicable and will not be used in the TTRFD derivation; otherwise C5 is considered met at

Data Source	Criteria	Date and Time when Criterion is Met
		
the latest stop date and time of IV antibiotics.
 
For C5, if IV antibiotics use ended before the first infusion (loading dose) of study drug, then C5 will be considered as having been met at the date and time of the start of first infusion (loading dose) of study drug.

	C6	
If a subject never received a RBC transfusion, then C6 is not applicable and will not be used in the TTRFD derivation; otherwise C6 is considered met at the latest stop date and time of RBC transfusion.
 
For C6, if RBC transfusion ended before the first infusion (loading dose) of study drug, then C6 will be considered as having been met at the date and time of the start of first infusion (loading dose) of study drug.

Derivation of TTRFD

STEP 1: For each subject, determine the date and time when each criterion is met, as shown in [Table 5](#) above.

STEP 2: Determine the date and time when RFD is achieved, ie, **[RFD date and time]** for each subject.

[RFD date and time]

= Latest of the dates and times when the applicable criteria among C1-C6 are met (using [Table 5](#))

STEP 3: Determine the TTRFD for each subject.

TTRFD for a subject (in hours)

= **[RFD date and time]** – **[Date and time of start of 1st infusion (loading dose) of study drug]**

Details on the handling of missing TTRFD data components or TTRFD censoring rules are provided in [Section 7.1](#).

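### Haemoglobin shift tables (SAP 10.3) use only End of Treatment and Day 35, with no visible transfusion rule, so a transfused fall can appear as no shift or an improvement

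*SAP*

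**What the plan says.** - **Shift tables.** SAP 10.3: "shift tables will be generated showing the shift at End of treatment and at the Day 35 post-discharge follow-up visit". Haemoglobin is graded 0 (above 11 g/dL), 1 (above 9 to 11), 2 (above 7 to 9), 3 (5 to 7) and 4 (below 5).
- **Scheduled sampling.** Protocol 7.2.3: "The following laboratory tests will be performed locally during the study at the VOC/Treatment-Ready Screening visit, End of Treatment, and the Day 35 Post-Discharge". Nothing is scheduled between screening and End of Treatment.
- **Unscheduled sampling.** The same section allows it: "Unscheduled clinical labs may be obtained at any time during the study to assess any perceived safety concerns". No visible text gives these results a place in the shift table.
- **Timing of the End of Treatment sample.** Protocol 6.2.3: "The following End of Treatment procedures are to be performed within 24 hours after the last dose of study drug". This can be as late as Day 8.
- **Transfusion.** Protocol 5.8.5 lists conditions arising in hospital that may lead to transfusion. They include symptomatic anaemia and "worsening of anemia with an inadequate reticulocyte response".
- **Transfusion data.** Stop times are recorded in the eCRF and enter the primary endpoint. SAP 6.1.1, Table 5: "otherwise C6 is considered met at the latest stop date and time of RBC transfusion".
- **Other laboratory outputs.** Protocol 2.2.2 and SAP 6.2 name the incidence of laboratory abnormalities and the change from baseline at end of treatment. SAP 8.5 adds summaries under the sponsor's reporting standards.

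**The concern.** Transfusion happens after randomisation and is prompted by the quantity being tabulated. After it, the End of Treatment haemoglobin partly reflects donor cells, so the table can record the treatment of a fall and miss the fall itself. Change from baseline at end of treatment rests on the same sample and has the same weakness. If the arms were transfused at different rates, both summaries would lean towards reassurance for the arm transfused more often. The safety outputs visible in SAP 8.5 do not count transfused subjects by arm, so a reader of the tables could not see this.

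Haemoglobin deserves a clear table because Protocol 1.2.3 reports one event above Grade 2 on rivipansel in the three Phase 1 studies: "Severe symptomatic anemia (Grade 4) that occurred in 1 subject with stable SCD". It was judged only remotely related and resolved with therapy. That is a reason to look carefully, not evidence of a drug effect.

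**Working it through.** The plan states no figure on this point, so there is nothing to reproduce. The check applies the SAP 10.3 grades to a baseline, a nadir and a value after transfusion.

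**Inputs**
- Grade bands: SAP 10.3.
- Baseline: taken as the screening value, the only scheduled haematology before dosing. Protocol 4.2 excludes "Hemoglobin <5 gm/dL", so an eligible subject starts at grade 0 to 3 and any grade 4 on study is a true worsening.
- Rise in haemoglobin from nadir to the End of Treatment sample: **an assumption, not in the documents**, ranged from 0.5 to 3.0 g/dL.

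**Formula.** Reported shift = grade(nadir + rise) − grade(baseline). Positive means worse. The true shift at the nadir is grade(nadir) − grade(baseline).

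| Baseline | Nadir | True shift | Rise | End of Treatment | Reported shift |
|---|---|---|---|---|---|
| 6.8 (G3) | 4.9 (G4) | +1 | 0.5 | 5.4 (G3) | 0 |
| 6.8 (G3) | 4.9 (G4) | +1 | 2.0 | 6.9 (G3) | 0 |
| 6.8 (G3) | 4.9 (G4) | +1 | 3.0 | 7.9 (G2) | −1, improvement |
| 8.0 (G2) | 6.0 (G3) | +1 | 1.0 | 7.0 (G3) | +1, still worse |
| 8.0 (G2) | 6.0 (G3) | +1 | 1.5 | 7.5 (G2) | 0 |
| 8.0 (G2) | 6.0 (G3) | +1 | 2.0 | 8.0 (G2) | 0 |
| 9.5 (G1) | 6.5 (G3) | +2 | 2.0 | 8.5 (G2) | +1, still worse |
| 7.0 (G3) | 5.5 (G3) | 0 | 2.0 | 7.5 (G2) | −1, improvement |

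The last row shows a second limit. A fall of 1.5 g/dL inside grade 3 gives no shift even at the nadir, so a lowest-value table alone would miss it. A transfusion count is needed as well.

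**Dependence on the rise.** Take a grid in steps of 0.1 g/dL: baseline 6.0 to 11.0, fall 1.0 to 3.0, nadir 3.5 to 7.0, keeping only cells where the grade at the nadir is worse than at baseline. That leaves 570 cells. The share reported as no shift or an improvement is:

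| Rise (g/dL) | Cells | Share |
|---|---|---|
| 0.5 | 120/570 | 21% |
| 1.0 | 265/570 | 46% |
| 1.5 | 395/570 | 69% |
| 2.0 | 460/570 | 81% |
| 2.5 | 540/570 | 95% |
| 3.0 | 570/570 | 100% |

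These are equally weighted grid cells, not probabilities for patients. They show only that masking is neither rare nor automatic.

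**The case against.** The best reply is that this is one descriptive table among several safety outputs.

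- **Adverse events.** Under Protocol 8.5 a test result that needs intervention is reportable as an adverse event, so a transfused fall qualifies. It may also be serious under Protocol 8.6. Adverse events are summarised by arm under SAP 8.5. This stands, and the event need not be lost to the report. However, Protocol 8.8 rates severity by interference with function, so the adverse event record does not supply a haemoglobin grade.
- **Laboratory abnormalities.** Their incidence is a separate endpoint and may capture the nadir. This stands in part: the visible text does not say whether unscheduled or pre-transfusion values count.
- **Missing text.** SAP 10.2 is incomplete, and the change table in SAP section 1 says laboratory reporting details were added or updated across 10.1 to 10.3. A rule for unscheduled values may exist there. The point is therefore limited to the visible text. The visible rule in 10.2, which takes the most extreme value, works within one visit time point and gives physical examination and vital signs as its examples.
- **Agreement with the protocol.** The protocol itself names change from baseline at end of treatment. This stands, and is why the planned shifts should be kept.

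A reader might infer more than the documents support:
- *Every transfused fall is hidden.* With a small rise or a deep fall the table still shows worsening, as the working shows.
- *Haemoglobin safety as a whole is unassessed.* The routes above remain, and the external committee reviews safety data regularly.
- *Rivipansel lowers haemoglobin, at a rate that can be projected from Phase 1.* That rests on one event, judged remotely related. Protocol 1.2.3 reports comparable overall adverse event and serious adverse event rates across groups in the randomised Phase 2 trial.

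**Conclusion.** The point holds in limited form. On the visible text, following SAP 10.3 as written can show a fall that was transfused before the End of Treatment sample as no shift or an improvement. Change from baseline at End of Treatment is affected in the same way.

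The size depends on the rise after transfusion, which the documents do not give. The number of subjects affected cannot be estimated from the documents, because they give no transfusion rates.

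The conclusion assumes that the missing part of SAP 10.2 holds no rule that deals with this. The primary analysis, sample size and type I error are untouched. This is an inexpensive improvement to a safety table.

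**What to change.** Keep the planned End of Treatment and Day 35 shifts, and add to SAP 10.3:

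1. A shift from Baseline to the lowest haemoglobin from first infusion through End of Treatment, using all recorded values including unscheduled ones. Flag values obtained after a transfusion, but do not discard them. Restricting the table to pre-transfusion values would lose any later, deeper fall.
2. The number and percent of subjects with any RBC transfusion after the first infusion, by arm, with the exact 95% CI for the difference already specified for Tier-1 events in SAP 8.5. Identify these subjects in the haemoglobin shift tables.
3. A footnote marking subjects transfused before the first infusion. SAP Table 5 foresees this, and it can affect Baseline.

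If the missing part of SAP 10.2 already has a rule for unscheduled laboratory values, refer to it in 10.3.

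**Cost.** SAP wording, one derived flag and two short tables. Transfusion times are already collected for criterion 6. The lowest-value table has a real limit: unscheduled testing depends on care, and Protocol 7.2.3 does not say that every local result enters the database. Enrolment closed on 25 April 2019 (SAP section 1), so more complete collection cannot now be planned prospectively. A footnote should say so.
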